## Preclinical Data

[figure not shown]

Figure 2

As shown in Figure 2, the mTOR inhibitor INK128 (TAK-228) synergistically enhances the antiproliferative effect of tamoxifen in ER-positive MCF-7 breast cancer cells. Proliferation by WST-1 assay was assessed in cells treated with INK128, tamoxifen, or both for 96 h.

[figure not shown]

Figure 3

As shown in Figure 3, the tamoxifen-resistant ER-positive ZR75-30 cell line does not respond to tamoxifen treatment. INK128 alone at a concentration of 10  $\mu$ M significantly reduced proliferation. Proliferation by WST-1 assay was assessed in cells treated with INK128, tamoxifen, or both for 96 h.

## Rationale for Selected Dose and Schedules of TAK-228

### RP2D for milled TAK-228 Weekly Schedule: 30 mg p.o. QW

The selected RP2D of 30 mg TAK-228 QW is based on the findings from 2 studies: Study INK128-001 and Study MLN0128-1004.

Study INK128-001 was the first-in-human study of TAK-228. This was an open label study designed to determine the MTD and to identify dose-limiting toxicities (DLTs) for p.o. administration of single-agent unmilled TAK-228, and to characterize the safety and tolerability of escalating doses of TAK-228 in patients with advanced solid tumors. In this study, 116 patients with advanced solid tumors received TAK-228 (2 – 40 mg via 4 dosing schedules: QD (31 patients), QDx3 days per week (33 patients), QDx5 days per week (22 patients), and QW (30 patients) in the dose escalation phase. Doses of 40 mg QW, 30 mg QW, and 5 mg QD were further evaluated in an additional 82 patients in the expansion phase.

Improved tolerability, including a reduced frequency of TEAEs leading to dose interruptions and modifications, respectively (30 mg QW: 24% and 41%, vs 40 mg QW: 19% and 77% as of data cut off 9 December, 2015) and longer duration of clinical benefit favored 30 mg QW dosing as a RP2D and schedule for further development.

Scale-up manufacturing of TAK-228 capsules required the introduction of a physical milling step during the granulation process to control for particle size distribution of TAK-228 drug substance. In order to observe whether this milling step altered the safety and PK profile of TAK-228, the recommended dose of 30 mg milled TAK-228 QW was further evaluated and confirmed in Study MLN0128-1004 in which a total of 14 patients were enrolled and assigned, sequentially, to 2 QW dosing cohorts: 20 mg QW and 30 mg QW milled TAK-228 (see Table 6 below).

**TABLE 6 Dose-Limiting Toxicity Observed with Milled TAK-228 QW in Study MLN0128-1004**

Dose of Milled TAK-228	Number of Patients	Evaluable	Patients with DLTs observed in Cycle 1
20 mg QW	6		None
30 mg QW	6		None

DLT = dose-limiting toxicity; QW = once weekly.

As none of the patients in either dose cohort experienced DLT in Cycle 1, a dose of 30 mg milled TAK-228 QW, dosed in empty-stomach conditions was selected as RP2D for further development. No clinically meaningful differences in PK of TAK-228 were noted between the unmilled TAK-228 (Study INK128-001) and milled TAK-228 (Study MLN0128-1004) when given QW (further details available in the current IB version).

## **Innovation**

This proposal is innovative in various aspects. Firstly, it targets the ER with an FDA-approved compound (tamoxifen). Tamoxifen competitively binds to ERs on tumor cells and other tissue targets, producing a nuclear complex that decreases DNA synthesis and inhibits estrogen effects. Secondly, our proposal is highly relevant given that mTOR inhibitors are currently being investigated for the treatment of ER-positive endocrine-resistant breast cancer. Here, we propose an open label phase II study of TAK-228 in

combination with tamoxifen in patients with newly diagnosed ER-positive breast cancer. Use of TAK-228 plus tamoxifen is supported by strong data showing that this combination decreases ER-positive breast cancer cell proliferation and increases pCR in patients with newly diagnosed ER-positive breast cancer. Thirdly, the correlation of specific molecular markers (ER; Ki67; mitotic index; apoptosis; levels of S6K1, 4EBP-1, eukaryotic translation initiation factor (EIF)4E, EIF4G, and EIF4A; levels of phosphorylated S6K1, p53, p63, and p73; and p63 and p73 gene signatures) with clinical parameters such as tumor response will help define a biomarker signature associated with p63/p73 and/or PI3K/AKT dependence and NFkB in ER-positive breast cancers and identify new therapeutic options for patients with ER-positive breast cancers. All tissues collected during the study will be stored for future analyses including genomic analyses. Tumor biopsy specimens obtained at the time of first diagnosis and week 6 of treatment will be correlated with the surgical specimen. An additional biopsy will be obtained from patients whose disease progresses while on treatment.

## 7. STUDY OBJECTIVES

### 7.1 Primary Objective

- To evaluate Ki67 before and after treatment with the mTORC1/2 inhibitor TAK-228 plus the non-steroidal agent tamoxifen in patients with newly diagnosed ER-positive, HER2-negative breast cancer.

### 7.2 Secondary Objectives

- To evaluate the pCR rate after treatment with TAK-228 plus tamoxifen in patients with newly diagnosed ER-positive, HER2-negative breast cancer. pCR is defined as the absence of residual invasive and in situ cancer on hematoxylin and eosin evaluation of the complete resected breast specimen and all sampled regional lymph nodes following completion of neoadjuvant systemic therapy (i.e., ypT0 ypN0 in the current American Committee on Cancer staging system).
- To evaluate the PEPI score after treatment with TAK-228 plus tamoxifen in patients with newly diagnosed ER-positive, HER2-negative breast cancer.
- To assess the toxicity and safety of TAK-228 plus tamoxifen in patients with newly diagnosed ER-positive, HER2-negative breast cancer.

### 7.3 Tertiary/Exploratory Objectives

- To determine the plasma PK of the TAK-228 plus tamoxifen combination.
- To assess the correlation between pCR to TAK-228 plus tamoxifen and changes in tissue-based markers including Ki67, p53/p63/p73, PI3K/AKT/mTOR, and NFkB pathways in ER-positive, HER2-negative breast tumors.
- To assess tumor mutational status to identify predictors of response to the TAK-228 plus tamoxifen combination.
- To evaluate Oncotype DX recurrence score before and after treatment with TAK-228 plus tamoxifen.

## 8. STUDY ENDPOINTS

### 8.1 Primary Endpoint

[figure not shown]
The primary endpoint of this protocol is the change in Ki67 after treatment with TAK-228 plus tamoxifen in patients with newly diagnosed ER-positive, HER2-negative breast cancer.

### 8.2 Secondary Endpoints

Secondary endpoints include pCR rate, PEPI score, toxicity, and safety of TAK-228 plus tamoxifen in patients with newly diagnosed ER-positive, HER2-negative breast cancer.

### 8.3 Tertiary/Exploratory Endpoints

The exploratory endpoints include assessment of plasma PK of the TAK-228 plus tamoxifen combination and correlative markers in biopsies. The correlation between pCR to TAK-228 plus tamoxifen and changes in Ki67, p53/p63/p73, PI3K/AKT/mTOR, and NF $\kappa$ B pathways in ER-positive, HER2-negative breast tumors will also be assessed. Tumor mutational status will also be assessed to identify predictors of response to the TAK-228 plus tamoxifen combination. Oncotype DX recurrence score will be evaluated before and after treatment with TAK-228 plus tamoxifen.

## 9. STUDY DESIGN

### 9.1 Overview of Study Design

Open label phase II clinical trial to determine the efficacy (change in Ki67, pCR rate, and PEPI score), toxicity, and safety of TAK-228 plus tamoxifen in patients with newly diagnosed ER-positive, HER2-negative breast cancer.

Figure 4

## 9.2 Number of Patients

The calculated sample size is 35 patients, with enrollment considered the day the informed consent form (ICF) is signed.

## 9.3 Duration of Study

Patients will receive TAK-228 QW and tamoxifen QD for 16 weeks. Screening for inclusion in the study will be done within 28 days prior to the day 1 dose of TAK-228 and tamoxifen. Baseline vital signs, labs, physical exam, and biopsy and tumor tissue collection will be done within 7 days prior to the day 1 dose of TAK-228 and tamoxifen. Visits will occur at weeks 1, 3, 4, 6, 8, 12, and 16 and at end of treatment (7 to 10 days after the final dose of study treatment).

## 10. STUDY POPULATION

The study is designed for patients with newly diagnosed ER-positive, HER2-negative breast cancer. Written informed consent is required before performing any study-specific tests or procedures. Signing of the Informed Consent Form can occur outside the 28-day screening period. All screening evaluations must be completed and reviewed to confirm that patients meet all eligibility criteria before study entry. Results of standard-of-care tests or examinations performed prior to obtaining informed consent and within 28 days prior to study entry (except where otherwise specified) may be used for screening assessments rather than repeating such tests. The investigator will maintain a screening log to record details of all patients screened and to confirm eligibility or record reasons for screening failure, as applicable.

  - Agree to practice true abstinence, when this is in line with the preferred and usual lifestyle of the patient. (periodic abstinence [e.g., calendar, ovulation, symptothermal, postovulation methods] and withdrawal, spermicides only, and lactational amenorrhea are not acceptable methods of contraception. Female and male condom should not be used together).
  - Agree not to donate sperm during the course of this study or within 120 days after receiving their last dose of the study drugs;
7. Screening clinical laboratory values as specified below:
  - a) Bone marrow reserve consistent with: ANC  $\geq 1.5 \times 10^9/L$ , platelet count  $\geq 100 \times 10^9/L$ , and hemoglobin  $\geq 9 \text{ g/dL}$  (without transfusion) within 1 week preceding the administration of the study drugs;
  - b) Hepatic status: Serum total bilirubin  $\leq 1 \times \text{ULN}$  (in the case of known Gilbert's syndrome, a higher serum total bilirubin [ $> 1.5 \times \text{ULN}$ ] is allowed), aspartate aminotransferase (AST) and alanine aminotransferase (ALT)  $\leq 1.5 \times \text{ULN}$ , and alkaline phosphatase  $\leq 1.5 \times \text{ULN}$ ;
  - c) Renal status: Creatinine clearance  $\geq 50 \text{ mL/min}$  based on Cockcroft-Gault estimate or based on urine collection (12 or 24 hour);
  - d) Metabolic status: HbA1c  $< 7.0\%$ , FSG  $\leq 130 \text{ mg/dL}$ , and fasting triglycerides  $\leq 300 \text{ mg/dL}$ .
8. Ability to swallow oral medications.
9. Voluntary written consent must be given before performance of any study-related procedure not part of standard medical care, with the understanding that consent may be withdrawn by the patient at any time without prejudice to future medical care.
10. Negative serum pregnancy test within 7 days prior to the administration of the study drugs for women of childbearing potential.
11. Patient must be accessible for treatment and follow-up.
12. Patient must be willing to undergo breast biopsies as required by the study protocol.

## 10.2 Exclusion Criteria

Patients meeting any of the following exclusion criteria are not to be enrolled in the study:

1. Any patient with metastatic disease.
2. Other clinically significant comorbidities, such as uncontrolled pulmonary disease, active central nervous system disease, active infection, or any other condition that could compromise the patient's participation in the study.
3. Known human immunodeficiency virus infection.
4. Known hepatitis B surface antigen-positive or known or suspected active hepatitis C infection.
5. Any serious medical or psychiatric illness that could, in the investigator's opinion, potentially interfere with the completion of the protocol-specified treatment.
6. Diagnosed or treated for another malignancy within 2 years before administration of the first dose of the study drugs or previously diagnosed with another malignancy and have any evidence of residual disease. Patients with non-melanoma skin cancer or carcinoma in situ of any type are not excluded if they have undergone complete resection.
7. Breastfeeding or pregnant.

8. Manifestations of malabsorption due to prior GI surgery, GI disease, or an unknown reason that may alter the absorption of TAK-228. Patients with enteric stomata are also excluded.
9. Treatment with any investigational products within 2 weeks before administration of the first dose of the study drugs.
10. Poorly controlled diabetes mellitus (defined as HbA1c > 7%). Patients with a history of transient glucose intolerance due to corticosteroid administration may be enrolled in the study if all other inclusion criteria and none of the other exclusion criteria are met.
11. History of any of the following within the last 6 months before administration of the first dose of the study drugs:
  - Ischemic myocardial event, including angina requiring therapy and artery revascularization procedures
  - Ischemic cerebrovascular event, including transient ischemic attack and artery revascularization procedures
  - Requirement for inotropic support (excluding digoxin) or serious (uncontrolled) cardiac arrhythmia (including atrial flutter/fibrillation, ventricular fibrillation, and ventricular tachycardia)
  - Placement of a pacemaker for control of rhythm
  - New York Heart Association Class III or IV heart failure (see Appendix D)
  - Pulmonary embolism
12. Significant active cardiovascular or pulmonary disease including:
  - Uncontrolled hypertension (i.e., systolic blood pressure > 180 mm Hg, diastolic blood pressure > 95 mm Hg). Use of antihypertensive agents to control hypertension before week 1, day 1 is allowed.
  - Pulmonary hypertension
  - Uncontrolled asthma or O2 saturation < 90% by arterial blood gas analysis or pulse oximetry on room air
  - Significant valvular disease, severe regurgitation, or stenosis by imaging independent of symptom control with medical intervention or history of valve replacement
  - Medically significant (symptomatic) bradycardia
  - History of arrhythmia requiring an implantable cardiac defibrillator
  - Baseline QTc prolongation (e.g., repeated demonstration of QTc interval > 480 milliseconds or history of congenital long QT syndrome or torsades de pointes)
13. Patients receiving systemic corticosteroids (either IV or oral steroids, excluding inhalers or low-dose hormone replacement therapy) within 1 week before administration of the first dose of the study drugs.
14. Daily or chronic use of a proton pump inhibitor (PPI) and/or having taken a PPI within 7 days before receiving the first dose of the study drugs.
15. Patients unwilling or unable to comply with the study protocol.
16. Patients previously treated with hormonal therapy (tamoxifen, AI) or PI3K, AKT, dual PI3K/mTOR, TORC1/2, or TORC1 inhibitors.
17. Patients who are currently being treated with cancer therapy (chemotherapy, radiation therapy, immunotherapy, or biologic therapy) other than the trial therapy.
18. Patients with hypersensitivity to mTOR inhibitors or tamoxifen.

## 11. STUDY DRUG

### 11.1 Study Drug Administration

Current protocol-specific criteria for administration of TAK-228 must be met and documented before drug administration. Study drug will be administered only to eligible patients under the supervision of the investigator.

TAK-228 will be administered on an empty stomach. Patients should be instructed to refrain from eating and drinking (except for water and prescribed medications) for 2 hours before and 1 hour after each dose. Patients should drink at least 8 ounces (240 mL) of water with their TAK-228 dose. Patients should be instructed to take their study medication in the morning on each scheduled dosing day (day 1 of each week  $\pm$  1 day) and not to take more than the prescribed dose at any time. Patients should swallow the study medication whole and not chew it, open it, or manipulate it in any way before swallowing. If a patient does not take their TAK-228 dose on the scheduled dosing day (day 1 of each week  $\pm$  1 day), then this will be considered a missed dose. Patients should record any missed doses in their diary and resume drug administration at the next scheduled time with the prescribed dosage. Under no circumstance should a patient repeat a dose or double-up doses.

If severe emesis or mucositis prevents the patient from taking scheduled doses, that dose will be skipped. If emesis occurs after study medication ingestion, the dose will not be readministered, and patients should resume dosing at the next scheduled time with the prescribed dosage. Patients should record the occurrence of the emesis in their dosing diaries. Under no circumstance should a patient repeat a dose or double-up doses.

Tamoxifen will be administered by the patient pursuant of a prescription obtained from the patient's pharmacy. It is to be administered with or without food QD. Patients should be instructed to take their tamoxifen at approximately the same time each day and not to take more than the prescribed dose at any time. On TAK-228 scheduled dosing days, tamoxifen should be taken in the evening (before bed). Patients should swallow the tamoxifen whole and not chew it, crush it, or manipulate it in any way before swallowing.

#### 11.1.1 Dose Modification Guidelines

TAK-228 should be administered, unless the patient has a grade 3 or greater TAK-228-related event. Guidelines for dose interruption and dose reduction are described below.

#### 11.1.2 Criteria for Dose Interruption During a Cycle/Visit

TAK-228 should be withheld for treatment-related toxicities that are grade 3 or higher despite supportive treatment per standard clinical practice. If the event resolves to grade 1 (or grade 2 for hyperglycemia or rash) or to baseline values within 3 weeks of interrupting treatment, then the patient may resume study treatment at a dose level reduced by 1 level.

The following non-hematologic toxicities attributed to TAK-228 would not require dose interruption:

- Grade 3 or higher nausea and/or emesis in the absence of optimal antiemetic prophylaxis (optimal antiemetic prophylaxis is defined as an antiemetic regimen that employs both a serotonin type 3 receptor antagonist and a corticosteroid given in standard doses and according to standard schedules)
- Grade 3 or higher diarrhea that occurs in the absence of optimal supportive therapy
- Grade 3 fatigue

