**TABLE 13 MANAGEMENT OF LEFT VENTRICULAR DYSFUNCTION**

Grade	Description	Dose Modification
1	Asymptomatic decline in: LVEF >15% from baseline values, OR LVEF >10% to 15% from baseline values and is below institution's LLN.	No change; continue TAK-228 at the same dose and schedule.
≥2	Symptomatic cardiac dysfunction/congestive heart failure.	Discontinue treatment.

LLN=lower limit of normal; LVEF=left ventricular ejection fraction.

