**TABLE 15 MANAGEMENT OF OTHER NON-HEMATOLOGIC TOXICITIES (INCLUDING ASTHENIA, WEAKNESS, AND FATIGUE)**

Grade	Description	Treatment	Dose Modification
1	Mild; asymptomatic or mild symptoms; clinical or diagnostic observations only; intervention not indicated.	Initiate appropriate medical therapy and monitor.	If tolerable, then no adjustment is required.
2	Moderate; minimal, local or noninvasive intervention indicated.	Initiate appropriate medical therapy and monitor.	
 
• If tolerable, then no adjustment required.
 
• If toxicity becomes intolerable, hold TAK-228 until recovery to ≤grade 1, then reinitiate at the same dose.
 

≥ 3	Severe or medically significant but not immediately life-threatening; hospitalization or prolongation of hospitalization indicated.		Hold TAK-228 until recovery to ≤grade 1. Reinitiate TAK-228 at dose reduced by 1 level.  Patients who develop grade 4 non-hematological toxicities (with the exception of isolated non-clinically significant laboratory values) should permanently discontinue study treatment, unless they derive clinical benefit, in which case they may be retreated at a reduced dose level after recovery to ≤grade 1 severity.

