**TABLE 17 MANAGEMENT OF NON-INFECTIOUS PNEUMONITIS**

Grade	Description	Treatment	TAK-228 Dose Modification
1	Asymptomatic: Radiographic findings only.	Rule out infection and closely monitor.	None
2	Symptomatic: Not interfering with activities of daily living.	Rule out infection and consider treatment with corticosteroids until symptoms improve to ≤grade 1.	Interrupt TAK-228 
 
When symptoms ≤grade 1, reinitiate TAK-228 at a dose reduced by 1 level. If no recovery within 3 weeks (21 days), then discontinue TAK-228.
 

3	Symptomatic: Interfering with activities of daily living; Requires administration of oxygen.	Rule out infection and consider treatment with corticosteroids until symptoms improve to ≤grade 1.	Interrupt TAK-228 until symptoms resolve to ≤grade 1. 
 
Consider reinitiating TAK-228 at a dose reduced by 1 level.
 
If toxicity recurs at grade 3, discontinue TAK-228.
 

4	Life-threatening: Ventilatory support indicated.	Rule out infection and consider treatment with corticosteroids.	Discontinue TAK-228.

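### The 11.1.2 list of toxicities exempt from TAK-228 interruption contradicts Tables 12 and 15, and no order of precedence is stated

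*Combined protocol and SAP*

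**What the plan says.** Section 11.1 gives general dosing rules and section 11.6 gives tables by event.

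- **Section 11.1.1:** "TAK-228 should be administered, unless the patient has a grade 3 or greater TAK-228-related event". The next sentence is a pointer: "Guidelines for dose interruption and dose reduction are described below".
- **Section 11.1.2, trigger:** "TAK-228 should be withheld for treatment-related toxicities that are grade 3 or higher despite supportive treatment per standard clinical practice".
- **Section 11.1.2, exemptions:** under the line "The following non-hematologic toxicities attributed to TAK-228 would not require dose interruption" come three items. They are grade 3 or higher nausea or emesis without optimal antiemetic prophylaxis, grade 3 or higher diarrhea without optimal supportive therapy, and "Grade 3 fatigue". The first two carry a condition; the third carries none.
- **Table 15 (section 11.6.7):** it covers other non-hematologic toxicities and names asthenia, weakness and fatigue in its title. At grade 3 or higher: "Hold TAK-228 until recovery to ≤grade 1. Reinitiate TAK-228 at dose reduced by 1 level".
- **Table 12 (section 11.6.5):** for nausea or vomiting of grade 3 or higher it holds TAK-228 whether the episode lasts up to 72 hours or longer. Only the longer-duration instruction mentions optimal therapy.
- **Table 17 (section 11.6.9):** it interrupts TAK-228 at grade 2 pneumonitis, and then "When symptoms ≤grade 1, reinitiate TAK-228 at a dose reduced by 1 level".
- **Table 13 (section 11.6.6):** it stops treatment at grade 2 or higher left ventricular dysfunction, described as "Symptomatic cardiac dysfunction/congestive heart failure".

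Sections 13.1.3 and 13.1.8 plan to report how often doses are interrupted and reduced.

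**The concern.** The conflict is about whether a dose is given at all. An investigator who reads the exemption list may keep dosing through grade 3 fatigue; one who turns to the table named for fatigue must hold and then reduce. Neither has departed from the protocol as written on the page in hand.

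Two things are at stake. The first is that a patient's exposure should not depend on which page is open. The second is the meaning of the planned interruption and reduction frequencies: if the trigger is ambiguous, those counts mix tolerability with the choice of rule, and the reader of the report cannot separate the two.

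**Working it through.** The protocol states no figure to reproduce here, so the first check is a side-by-side reading.

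| Event and grade | Sections 11.1.1 and 11.1.2 | Event table | Result |
|---|---|---|---|
| Fatigue, grade 3 | No interruption required, no condition attached | Table 15: hold, then restart one level lower | Direct conflict |
| Nausea or emesis, grade 3 or higher, prophylaxis not optimal, up to 72 hours | No interruption required | Table 12: hold, then resume without dose change | Direct conflict |
| Diarrhea, grade 3 or higher, supportive therapy not optimal | No interruption required | No table of its own; falls under the other toxicities of Table 15: hold, restart one level lower | Conflict by inference |
| Pneumonitis, grade 2 | Below the grade 3 threshold | Table 17: interrupt | Poor fit |
| Left ventricular dysfunction, grade 2 | Below the grade 3 threshold | Table 13: discontinue | Poor fit |

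All three entries on the exemption list therefore meet a table that holds the drug. The usual principle that specific text overrides general text does not settle fatigue: the 11.1.2 entry names one toxicity at one grade, while Table 15 covers a whole class, so the 11.1.2 entry is at least as specific. No sentence ranks the sections.

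The effect on one patient's exposure can be illustrated for fatigue.

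*Inputs from the protocol:* 16 weekly doses (Table 1); 30 mg at dose level 0 and 20 mg at level -1 (Table 7).

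*Assumptions:* two doses are missed before recovery to grade 1; no second reduction; under 11.1.2 the investigator continues in full.

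*Formula under Table 15:* with k doses given before onset and m missed, total = k × 30 + (16 − k − m) × 20 mg.

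- Section 11.1.2, dosing continued: 16 × 30 = 480 mg; no interruption, no reduction recorded.
- Table 15, onset after the week 3 dose: 3 × 30 + 11 × 20 = 310 mg; 1 − 310/480 = 35% less.
- Table 15, onset after the week 12 dose: 12 × 30 + 2 × 20 = 400 mg; 1 − 400/480 = 17% less.

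In both Table 15 cases the record shows one interruption and one reduction, against none under 11.1.2.

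**The case against.** The strongest reply is that most of this is general text giving way to specific tables. Section 11.1.1 points to guidelines that follow. Section 11.1.2 says when to withhold, not that holding below grade 3 is forbidden. The text after Table 7 permits interruptions and reductions for drug-related toxicity without any grade floor. Sections 11.6.6 and 11.6.9 introduce Tables 13 and 17 as the dose guidance for those events, and section 4.1.5 asks for a conservative approach to pneumonitis. This reply largely stands for the grade 2 events. A reader might infer that section 11.1 instructs sites to dose through grade 2 pneumonitis or cardiac dysfunction. The documents do not support that; what remains is loose wording in 11.1.1 and no statement of precedence.

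For diarrhea, the exemption agrees with the general trigger in 11.1.2, which applies only despite supportive treatment, and Table 15 never names diarrhea. That limb is weaker than the other two.

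For fatigue and nausea the reply fails. Reading the exemption as merely permissive does not help, because the tables instruct a hold. It does limit the size: an investigator may still interrupt under 11.1.2, so 480 mg is the upper end. With weekly dosing, a short hold for nausea may also cost no dose if recovery comes before the next dosing day.

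A reader might also infer that the conflict will arise often, since section 3.2 lists fatigue among the most common events. That list is regardless of causality and regimen and gives no grade. Severe-fatigue figures appear only for other treatments: 4% (grade 3 or 4) with everolimus plus exemestane in section 6 and 2% with tamoxifen in Table 4. Carried over purely as an assumption, they give 35 × 0.02 = 0.7 to 35 × 0.04 = 1.4 patients. Differences between sites are equally conditional, since section 14.2 mentions multiple sites only as a possibility.

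**Conclusion.** The exemption list in 11.1.2 contradicts the event tables: directly for grade 3 fatigue (Table 15) and for grade 3 or higher nausea or emesis without optimal prophylaxis (Table 12), and by inference for diarrhea. The mismatch between the 11.1.1 threshold and Tables 13 and 17 is a minor point of wording and precedence.

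For a single patient with grade 3 fatigue the difference is 80 to 170 mg of a planned 480 mg (480 − 400 and 480 − 310) under the stated timing, with two missed doses and full dosing otherwise. This is an example, not an expected average, and its frequency in this trial is unknown.

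The affected outputs are the descriptive safety summaries. Sample size and power are untouched, and no effect on the Ki67 analysis has been shown. The point should be corrected, but it does not put the primary analysis in question.

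**What to change.** Reconcile sections 11.1.1 and 11.1.2 with Tables 12, 13, 15 and 17 so that each event and grade carries one hold instruction. Add one sentence saying whether the general text or the event table governs if they differ. The reconciliation should cover all three items on the exemption list; correcting fatigue and diarrhea alone would leave the conflict with Table 12 in place. Which instruction stands is for the sponsor's clinical team, and this review takes no position on it.

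The cost is wording in a single amendment. No patients, visits or procedures are added. If patients have already been treated, it would help to note in the safety report which rule was applied to any grade 3 or higher fatigue, nausea, emesis or diarrhea before the change.
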